3. INVESTIGATIONAL PLAN

3.1 Study Design and Duration

This is a Phase 2, multi-center, open-label, multiple cohort study of elotuzumab in combination with pomalidomide and low-dose dexamethasone (EPd Cohort) and elotuzumab in combination with nivolumab (EN Cohort) to assess the safety and efficacy of these combination therapies for treatment of relapsed or refractory MM patients.

In the EPd Cohort, subjects will receive treatment with elotuzumab in combination with pomalidomide and low-dose dexamethasone in a 28 day cycle. Subjects will receive 10 mg/kg IV elotuzumab on Days 1, 8, 15, and 22 of Cycles 1 and 2. Starting with Cycle 3, subjects will receive 20 mg/kg on Day 1.

As of Amendment 02, subjects will also be enrolled in the EN cohort to receive a combination of elotuzumab and nivolumab in a 28-day cycle. EN subjects will receive nivolumab 240 mg IV on Days 1 and 15 for Cycles 1-4. At Cycle 5 and beyond, subjects will receive 480 mg IV on Day 1. Subjects will also receive elotuzumab 10 mg/kg on Days 1, 8, 15, and 22 of Cycles 1 and 2. At Cycle 3 and beyond, subjects will receive 20 mg/kg of elotuzumab IV on Day 1. If subjects do not achieve clinical benefit represented by at least minimal response (\geq MR) after 2 cycles of treatment or do not achieve an objective response (\geq PR) after 5 cycles of treatment, they may cross over to the EPd cohort at Day 1 of the subsequent cycles if they also meet the eligibility criteria for cross-over specified in Section 3.3.4.

Subjects will continue treatment as long as the subject has clinical benefit from the treatment and do not meet criteria for discontinuation.

All subjects will be assessed for safety and response as presented in the Time and Event Tables in Section 5. Subjects who are discontinued from further study treatment for reasons other than progression will be followed for disease progression. Following disease progression, subjects will be followed at least annually for survival.

Approximately 120 subjects will be screened in this study. A minimum of 60 subjects will be treated in the EPd Cohort. Approximately 30 subjects will be treated in the EN Cohort. The estimated duration of enrollment is 18 to 24 months, and the duration of the study is estimated at 48 months from the date of first patient, first visit. Per Revised Protocol 03, the EPd cohort is closed for enrollment.

The study design schematic is presented in Figure 3.1-1.

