4.5.2 Dexamethasone

Dexamethasone for subjects in the EPd cohort will be administered as indicated in Table 4.5.2-1.

Age	Day	1	8	15	22
Cycles 1 and 2					
\leq 75 years old	Dexamethasone (mg)	28 mg PO + 8 mg IV ^{a,b}			
> 75 years old	Dexamethasone (mg)	8 mg PO + 8 mg IV ^{a,b}			
Cycles 3 and beyo	ond				
\leq 75 years old	Dexamethasone (mg)	28 mg PO + 8 mg IV ^{a,b}	40 mg PO per week ^c	40 mg PO per week ^c	40 mg PO per week ^c
> 75 years old	Dexamethasone (mg)	8 mg PO + 8 mg IV ^{a,b}	20 mg PO per week ^c	20 mg PO per week ^c	20 mg PO per week ^c

Table 4.5.2-1:Dexamethasone Dosing, EPd Cohort

¹ On days of elotuzumab, infusion dexamethasone will be administered as a split dose of:

28 mg PO, for subjects \leq 75 years old or 8 mg PO for subjects > 75 years old (between 3 - 24 hours before the start of elotuzumab infusion)

8 mg IV (on the day of elotuzumab infusion at least 45 minutes before the start of infusion)

^b If elotuzumab dosing is skipped or discontinued, dexamethasone will be administered orally as in days without elotuzumab.

^c Note the dexamethasone dose, as elotuzumab is not given on Days 8, 15 and 22 of cycle 3 and beyond.

AND

At the investigator's discretion, the oral dexamethasone may be given as a split dose over 2 consecutive days. Dexamethasone delay should be performed as clinically indicated at the discretion of the investigator.

Dexamethasone for subjects in the EN cohort will be administered as indicated in Table 4.5.2-2.

Table 4.5.2-2:Dexamethasone Dosing: EN Cohort

Age	Day	1	8	15	22	
Cycles 1 and 2						
All subjects	Dexamethasone (mg)	8 mg IV ^{a,b}				
Cycles 3 and beyond						
All subjects	Dexamethasone (mg)	8 mg IV ^{a,b}				

^a On days of elotuzumab, dexamethasone will be administered as a premedication at dose of 8 mg IV at least 45 minutes before the start of infusion)

^b If elotuzumab dosing is skipped or discontinued, dexamethasone will be not be administered.

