4.5.3.1 Premedication Before Elotuzumab in Subjects Without a Prior Infusion Reaction

On weeks of elotuzumab infusion, the dexamethasone dose for the EPd cohort will be split into a PO and IV administration (described in Section 4.5.2), which will also serve as premedication for elotuzumab.

Intravenous and PO dexamethasone doses are calculated to provide a total dose that is bioequivalent to an oral dose of 40 mg (subjects who are \leq 75 years old) or 20 mg (in subjects who are > 75 years old). (Dexamethasone 8 mg IV is approximately bioequivalent to 11 mg PO).

For the EN cohort, dexamethasone will still be administered as a premedication for elotuzumab at a dose of 8 mg IV 45-90 minutes prior to initiating the elotuzumab infusion.

In addition, the following must also be administered 45 to 90 minutes before initiating the elotuzumab:

- H1 blocker: diphenhydramine (25 50 mg PO or IV) or equivalent
- H2 blocker: ranitidine (50 mg IV) or equivalent (eg, 150 mg PO)
- Acetaminophen (650 1000 mg PO)

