The pomalidomide dose intensity, per subject, will be calculated as:

7x[cumulative dose of pomalidomide / (min(date of first dose of Pomalidomide in the last cycle in which Pomalidomide was administered+28, discontinuation date, death date) - date of first dose of Pomalidomide)]

The relative dose intensity of pomalidomide is the dose intensity per week divided by the planned dose intensity per week, 21mg times 100%.

Dexamethasone:

The dose intensity (mg/week) of dexamethasone, per subject, will be calculated separately for the period encompassing Cycles 1 and 2 and for the periods from Cycles 3 and beyond.

Cycle 1 and 2:

7x[cumulative dose of Dexamethasone during the first 2 cycles/ (min(date of first dose of Dexamethasone in the last cycle among the first 2 cycles+28, discontinuation date, death date) - date of first dose of Dexamethasone in cycle 1)]

Cycle 3 and beyond:

7x[cumulative dose of Dexamethasone staring from Cycle 3 / (min(date of first dose of Dexamethasone in the last cycle+28, discontinuation date, death date) - date of first dose of Dexamethasone in cycle 3)]

Age	Day	1	8	15	22
Cycles 1 and 2			•		
\leq 75 years old	Dexamethasone	28 mg PO +			
	(mg)	8 mg IV ^{a,b}			
> 75 years old	Dexamethasone	8 mg PO +			
	(mg)	8 mg IV ^{a,b}			
Cycles 3 and bey	ond				
≤ 75 years old	Dexamethasone	28 mg PO +	40 mg PO per	40 mg PO per	40 mg PO per
	(mg)	8 mg IV ^{a,b}	week ^c	week ^c	week ^c
> 75 years old	Dexamethasone	8 mg PO +	20 mg PO per	20 mg PO per	20 mg PO per
	(mg)	8 mg IV ^{a,b}	week ^c	week ^c	week ^c

Table 3: Dexamethasone Dosing, All Subjects Receiving Elotuzumab

^a On days of elotuzumab, infusion dexamethasone will be administered as a split dose of:

28 mg PO, for subjects \leq 75 years old or 8 mg PO for subjects > 75 years old (between 3 - 24 hours before the start of elotuzumab infusion)

AND

8 mg IV (on the day of elotuzumab infusion at least 45 minutes before the start of infusion)

^b If elotuzumab dosing is skipped or discontinued, dexamethasone will be administered orally as in days without elotuzumab.

^c Note the dexamethasone dose, as elotuzumab is not given on Days 8, 15 and 22 of cycle 3 and beyond.

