The relative dose intensity of dexamethasone is the dose intensity per week divided by the planned dose intensity per week times 100%. The planned dose of dexamethasone (indicated in table 3) on elotuzumab dosing days, 8 mg IV dexamethasone plus 28 mg oral dexamethasone, is equivalent to 38.56 mg of oral dexamethasone for subjects \leq 75 years old; similarly for subjects

> 75 years old, the planned dose on elotuzumab dosing days, 8 mg IV dexamethasone plus 8 mg oral dexamethasone, is equivalent to 18.56 mg of oral dexamethasone. The planned dose when dexamethasone is not being administered with elotuzumab is 40 mg per week for subjects \leq 75 years old and 20 mg per week for subjects > 75 years old.

Nivolumab:

The dose intensity (mg/week) of Nivolumab, per subject, will be calculated separately for the period encompassing Cycles 1 to 4 and for the periods from Cycles 5 and beyond.

Cycle 1-4:

7x[cumulative dose of Nivolumab during the first 4 cycles/ (min(date of first dose of Nivolumab in the last cycle among the first 4 cycles+28, discontinuation date, death date) - date of first dose of Nivolumab in cycle 1)]

Cycle 5 and beyond:

7x[cumulative dose of Nivolumab staring from Cycle 5 / (min(date of first dose of Nivolumab in the last cycle+28, discontinuation date, death date) - date of first dose of Nivolumab in cycle 5)]

The relative dose intensity of nivolumab is the dose intensity per week divided by the planned dose intensity per week, 120mg times 100%.

Descriptive statistics (n, mean, STD, median, min, max, q1 and q3) will be presented for the cumulative dose, and dose intensity of each agent. The number and percentage of subjects whose relative dose intensity falls into the following categories will be presented: \geq 90 %, 80% to < 90%, 70% to < 80%, 60% to < 70%, < 60%.

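### SAP Table 3 captions the EPd dexamethasone plan for all elotuzumab recipients; if its relative dose intensity rule is applied to EN, a subject dosed exactly per the EN table scores 7% to 57%

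*SAP*

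**What the plan says.** Protocol 4.5.2 has two dexamethasone plans. Table 4.5.2-1 is captioned "Dexamethasone Dosing, EPd Cohort". It gives 28 mg PO (75 or under) or 8 mg PO (over 75) plus 8 mg IV on elotuzumab days, and 40 or 20 mg PO in weeks without elotuzumab. For the other cohort, "Dexamethasone for subjects in the EN cohort will be administered as indicated in Table 4.5.2-2". That table has a single row for all ages in each period, and its footnotes read "On days of elotuzumab, dexamethasone will be administered as a premedication at dose of 8 mg IV" and "If elotuzumab dosing is skipped or discontinued, dexamethasone will be not be administered". Protocol 4.5.3.1 agrees: "For the EN cohort, dexamethasone will still be administered as a premedication for elotuzumab at a dose of 8 mg IV".

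SAP 7.4.1.10, Table 3, reproduces the EPd schedule, including the EPd footnote that dexamethasone goes fully oral when elotuzumab is skipped. Its caption, however, is "Dexamethasone Dosing, All Subjects Receiving Elotuzumab". The text then fixes the RDI denominator from that table: "The planned dose of dexamethasone (indicated in table 3) on elotuzumab dosing days, 8 mg IV dexamethasone plus 28 mg oral dexamethasone" is converted to 38.56 mg oral-equivalent. The figure for subjects over 75 is 18.56 mg, and weeks without elotuzumab count as 40 or 20 mg. The rule distinguishes age but not cohort.

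SAP 7.1 states that the EPd and EN cohorts are analysed separately. SAP 7.4.1.10 includes nivolumab dose intensity, so the section is not confined to EPd. It contains no EN dexamethasone plan and does not exclude EN from the dexamethasone RDI.

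**The concern.** Every EN subject receives elotuzumab and so falls under the caption of Table 3. A programmer who follows the caption and the age-only rule would divide the EN premedication dose by the EPd treatment dose. The resulting EN exposure table would place subjects who received what Table 4.5.2-2 specifies in the band below 60% of plan. It could not separate them from subjects whose doses were really omitted, and a reader would take it for poor delivery of treatment.

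**Working it through.** **Inputs**
- IV-to-oral factor: 1.32 (SAP 7.4.1.10).
- EN dose: 8 mg IV per elotuzumab day, none otherwise (protocol Table 4.5.2-2).
- EN elotuzumab days: four per 28-day cycle in Cycles 1 and 2 ("Subjects will also receive elotuzumab 10 mg/kg on Days 1, 8, 15, and 22 of Cycles 1 and 2", protocol 3.1), then one per cycle from Cycle 3.
- Dose intensity: 7 × cumulative dose / days, computed separately for Cycles 1-2 and Cycles 3 and beyond (SAP 7.4.1.10).
- RDI: dose intensity / planned dose intensity × 100%.

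**The SAP's own figures.** 8 × 1.32 = 10.56. Then 28 + 10.56 = 38.56 and 8 + 10.56 = 18.56. Both reproduce exactly, so the arithmetic is right; the question is which subjects it covers.

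**Planned weekly dose under Table 3.** In Cycles 1-2 every week has elotuzumab, so the plan is 38.56 or 18.56 mg/week. From Cycle 3, one week in four has elotuzumab, and averaging over the cycle gives:
- 75 or under: (38.56 + 3 × 40)/4 = 158.56/4 = 39.64 mg/week.
- Over 75: (18.56 + 3 × 20)/4 = 78.56/4 = 19.64 mg/week.

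**Dose intensity of an EN subject dosed per Table 4.5.2-2, complete cycles**
- Cycles 1-2: 7 × (8 × 10.56)/56 = 10.56 mg/week.
- Cycles 3 and beyond: 7 × 10.56/28 = 2.64 mg/week.

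**RDI**

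| Age | Cycles 1-2 | Cycles 3 and beyond |
|---|---|---|
| 75 or under | 10.56/38.56 = 27.4% | 2.64/39.64 = 6.7% |
| Over 75 | 10.56/18.56 = 56.9% | 2.64/19.64 = 13.4% |

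**Sensitivity**
- Unrounded factor 1/0.76 (the bioavailability behind the 1.32): range 6.6% to 56.8%.
- Protocol 4.5.3.1's approximation of 8 mg IV to 11 mg PO: range 6.9% to 57.9%.
- Pooling 3 to 24 cycles: 8% to 20% (75 or under) and 17% to 42% (over 75).
- Stopping 7 to 14 days after a single Cycle 3 dose: the later-period value rises to 13%-27% (75 or under) or 27%-54% (over 75).

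None of these reaches 60%.

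**Cohort-matched denominator.** With the Table 4.5.2-2 plan as denominator (10.56 mg/week, then 10.56/4 = 2.64 mg/week), the same subject scores 100% in both periods and both age groups.

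**The case against.** The strongest reply is that the SAP never says an EN dexamethasone RDI will be produced. Much of the surrounding exposure text was written for EPd. SAP Table 2 shows only pomalidomide, elotuzumab and dexamethasone. Treatment duration in 7.4.1.1 covers those three drugs and omits nivolumab. Section 7.4.1.9 concerns oral dexamethasone, which Table 4.5.2-2 does not contain, and 7.4.4 speaks of two other study drugs. Nivolumab intensity was added only at SAP version 2.3, and the actual tables sit in a Data Presentation Plan that is not among the documents. This stands as far as it goes: the error is conditional on the rule being applied to EN. But the caption points the other way, separate EN analyses are required, and nothing excludes EN.

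A reader might also infer that essentially the whole EN cohort would fall below 60%. The documents do not support that, for two reasons.

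- **Crossover.** EN subjects without sufficient response may switch after 2 or 5 cycles (protocol 3.1, 3.3.4) and then follow the EPd schedule for Cycle 3 and beyond (protocol Table 4.5-1, footnote b). After the switch, the Table 3 plan is the matching denominator.
- **Premedication table.** Protocol Table 4.5.3.2-1 lists oral plus IV dexamethasone without naming a cohort, and its first row covers subjects with no prior reaction. Read literally for EN, that row gives the Table 3 elotuzumab-day dose, so RDI would be 100% in Cycles 1-2 and 38.56/158.56 = 24% or 18.56/78.56 = 24% later. For infusions after a reaction it gives, per elotuzumab day:
  - over 75, prior Grade 2: 8 + 10 × 1.32 = 21.2 mg, 114% of 18.56;
  - 75 or under, prior Grade 3: 16 + 18 × 1.32 = 39.76 mg, 103% of 38.56;
  - over 75, prior Grade 3: 4 + 12 × 1.32 = 19.84 mg, 107% of 18.56.

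That table conflicts with Table 4.5.2-2 and with 4.5.3.1, and the protocol does not say which governs EN. The conflict limits how widely the low percentages apply. It does not justify the Table 3 caption, because no protocol text gives EN the 40 or 20 mg oral weeks.

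Finally, RDI is descriptive. Protocol 4.7 monitors compliance through drug accountability and diaries, and no decision depends on RDI, so calling the result a compliance finding would go too far.

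**Conclusion.** The point holds as a protocol-SAP inconsistency in a denominator. Table 3 and the planned doses built on it are the EPd plan under a caption that takes in EN. Applied as written to EN, they give about 27% and 7% (75 or under) or 57% and 13% (over 75) for a subject dosed exactly per Table 4.5.2-2. The 7% and 57% extremes belong to different age groups and periods; they are not one subject's range.

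The figures rest on four assumptions: the rule is applied to EN, the subject has not crossed over, there has been no prior infusion reaction and Table 4.5.2-2 governs, and cycles are complete. The effect is confined to the exposure summary. PFS, ORR and the sample size are untouched. This is a minor correction, worth making because the wrong reading follows directly from the caption.

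**What to change.** 1. Recaption SAP Table 3, and restrict its planned doses and RDI denominator to EPd subjects and to crossover subjects from the switch onward. State that the denominator changes at crossover.
2. For EN before crossover, choose one of two statements. Either dexamethasone RDI is not reported, because it is premedication only, or it is computed against the protocol's own EN plan.
3. Before taking the second option, have the sponsor reconcile protocol Table 4.5.2-2 and 4.5.3.1 with Table 4.5.3.2-1, so that the EN plan used as denominator is unambiguous. Which passage governs is a clinical decision for the sponsor.
4. Limit Table 3's footnote on skipped elotuzumab to the same subjects, since the EN footnote says otherwise.

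In the SAP the cost is wording and one programming condition on cohort and crossover date. No new data are needed. The reconciliation in step 3 is a protocol clarification.

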7.4.2 Premedication Other than Dexamethasone for Hypersensitivity Reactions

A by-subject listing of pre-medication for elotuzumab, other than dexamethasone, will be provided for all treated subjects. This listing will be generated from the "Pre-medication for elotuzumab (other than Dexamethasone)" eCRF module and pre-medications will be coded using the BMS WHO drug dictionary.

7.4.3 Concomitant Medication

Concomitant medications are medications, other than study medication or pre-medications for elotuzumab recorded on the "Pre-medication for elotuzumab" eCRF page, which are taken by subjects any time on-study, no earlier than the first day of study drug and no later than 60 days after the last dose of study drug. Concomitant medications will be coded using the BMS WHO drug dictionary. If there is clear evidence to suggest that the medication stopped prior to the first dose of study medication, the medication will be assumed to be Prior only.

The number and percentage of subjects taking any concomitant medication and each medication (Anatomical Therapeutic Chemical [ATC] classification system drug name) will be summarized, overall and by treatment group.

A by subject listing of concomitant medication will be provided.

7.4.4 Discontinuation of Study Therapy

The number and percentage of subjects who have discontinued study treatment and reason for discontinuation will be summarized using the subject status eCRF page from end of treatment. This is done in order to give a full accounting of all subjects who are off study treatment.

In addition, for subjects who discontinued one drug, while continuing at least one of the other two study drugs, their reason for treatment discontinuation will be summarized based on the dose modification CRF. Subjects will be counted in this summary if there is evidence from the dosing CRF that the subject received the combination therapy in at least one cycle, followed by additional cycles, where one of the drugs in the combination was discontinued.

7.5 Efficacy

7.5.1 Progression-Free Survival

The primary analysis of this study is to estimate the two definitions of progression free survival (PFS) in all treated patients. The median PFS and 2-sided 95% confidence interval will be caculated via Kaplan-Meier (KM) estimation procedure. The PFS function will be estimated using the KM product limit method and will be displayed graphically. Estimates for 1-year, 2-year, and 3-year PFS rates will be presented along with their associated 95% CIs. These estimates will be come from the KM curve and their standard errors (SEs), for use in constructing CIs, will be computed using Greenwood's formula¹⁷ and on log-log transformation applied on the survivor function.

Analyses of PFS will be conducted based on all treated population, and also by subgroups based on lines of prior therapy (2L/3L groups), or by age group (<65 years, \geq 65 years), and (<75 years, \geq 75 years). Subgroup analysis by ECOG PS (0-1,2), by response to most recent line of therapy (relapsed and refractory, relapsed, refractory, intolerant) and by ISS stage (I,II,III) if albumin and beta 2 microglobulin data are available will be conducted as well. PFS is also evaluated based on 3 levels of response (VGPR or better, PR, SD or MR). PFS will be estimated using the Kaplan-Meier (KM) product limit method and presented using a KM curve.

Time from last tumor assessment to data cut-off in months will be summarized by treatment arm and overall for all treated subjects. Subjects who have a PFS event will be considered as current for this analysis.

A by-subject listing will be presented including PFS duration on all treated population, whether the subject was censored, and if censored, the reason.

All of the analyses will be repreated for primary and secondary definitions of PFS.

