4.1.3 Primary Definition of Progression-Free Survival

Progression Free Survival (PFS) is defined as the time from first dosing date to the date of the first documented progression per IMWG uniform criteria or death due to any cause, whichever occurs first. Subjects who die without a reported prior progression will be considered to have progressed on the date of their death. Subjects who did not progress or die will be censored on the date of their last adequate tumor assessment. Subjects who did not have any on study efficacy assessments and did not die will be censored on the first dosing date.

Subjects who switched to subsequent therapy prior to documented progression will be censored on the date of the last adequate tumor assessment prior to the initiation of the new therapy.

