4.2 Objective Response Rate (ORR)

The best overall response is determined as the best assessment based on all on-study efficacy data for the subject. Overall Response Rate (ORR) is defined as proportion of subjects with a best overall response of partial response (PR) or better.

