4.3 Overall Survival (OS)

Overall Survival (OS) is defined as the time from first dosing date to the date of death from any cause. A subject who has not died will be censored at last known date alive.

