7 STATISTICAL ANALYSES

7.1 General Methods

Continuous variables will be summarized using descriptive statistics; i.e. number of non-missing observations (n), mean, standard deviation (STD), median, minimum, maximum, first quartile

and third quartile. The number of decimal places displayed in all listings will be determined by the number of decimal places in the raw data. Unless otherwise specified, minimum and maximum will be reported to the precision as the data collected, one more decimal place for the mean and median, and two more decimal places for the standard deviation. The adjusted geometric mean, geometric mean ratio and the lower and upper limits of confidence interval will be displayed to three decimal places. Categorical variables will be summarized by frequencies and percentages.

Safety analyses will be conducted on all treated subjects. Efficacy analyses will be conducted on all treated subjects, and also by subgroups based on lines of prior therapy (2L, 3L), or by age group (<65 years, \geq 65 years), and (<75 years, \geq 75 years). Descriptive statistics (n, mean, median, standard deviation, minimum, maximum or interquartile range) will be provided. Because the sample size for the study is small, summary statistics with their associated 95% confidence intervals and tests of hypotheses will be based, to the extent possible, using small-sample statistics like the Clopper- Pearson for binomial data. Median time-to-event and its 95% confidence interval will be based on the Kaplan-Meier (KM) estimation procedure. The KM curves will be presented for time to event endpoints. Separate analyses will be conducted for each cohort EPd and EN.

Laboratory results, adverse events, and other symptoms will be graded using the National Cancer Institute (NCI) Common Terminology Criteria for Adverse Events (CTCAE), version 3.0, except where CTCAE grades are not available. Individual laboratory values will be presented in both the International System of Units (SI) and US unit (US). Adverse events will be categorized using the most current version of Medical Dictionary for Regulatory Activities (MedDRA), by system organ class and preferred term. Prior therapies will be summarized using the most current version of the World Health Organization (WHO) drug dictionary.

Statistical analyses will be carried out in SAS (Statistical Analysis System, SAS Institute, North Carolina, USA), unless otherwise indicated.

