7.5.2 Overall Survival

One of the secondary objective of this study is to estimate the overall survival (OS) in all treated subjects. The median OS and 2-sided 95% confidence interval will be calculated via Kaplan-Meier (KM) estimation procedure. The survival function will be estimated using the KM product limit method and will be displayed graphically. Estimates for 3-year, 4-year, and 5-year OS rates will be presented along with their associated 95% CIs. These estimates will be come from the

KM curve and their standard errors (SEs), for use in constructing CIs, will be computed using Greenwood's formula¹⁷ and on log-log transformation applied on the survivor function.

Analyses of OS will also be conducted based on all treated population, and also by subgroups based on lines of prior therapy (2L/3L groups), or by age group (<65 years, \geq 65 years), and (<75 years, \geq 75 years). Subgroup analysis by ECOG PS (0-1,2), by response to most recent line of therapy (relapsed and refractory, relapsed, refractory, intolerant) and by ISS stage (I,II,III) if albumin and beta 2 microglobulin data are available will be conducted as well. OS is also evaluated based on 3 levels of response (VGPR or better, PR, SD or MR). OS will be estimated using the Kaplan-Meier (KM) product limit method and presented using a KM curve.

Currentness of OS data will be summarized in months, by computing the time from "last known alive" date to data cut-off date. Subjects who have a death event will be considered as current for this analysis.

A by-subject listing will be presented including OS duration, whether the subject was censored, and if censored, the reason, for all enrolled subjects.

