7.5.3 Objective Response

The other secondary objective of this study is to estimate the Objective Response Rate (ORR). The number and percentage of subjects in each category of best overall response (stringent CR [sCR], complete response [CR], very good partial response [VGPR], partial response [PR], minor (minimal response) [MR], stable disease/no change [SD], progressive disease [PD], or unable to determine [UD]) will be presented. An estimate of the objective response rate and an associated exact two-sided 95% CIs (Clopper and Pearson¹⁸) will be presented. Also, the number and percentage of subjects in each category of best overall response according to the investigator tumor assessment will be presented.

Analyses of ORR will be conducted based on the all treated analysis population, and also by subgroups based on lines of prior therapy (2L, 3L), or by age group (<65 years, \geq 65 years), and (<75 years, \geq 75 years). Subgroup analysis by ECOG PS (0-1,2), by response to most recent line of therapy (relapsed and refractory, relapsed, refractory, intolerant) and by ISS stage (I,II,III) if albumin and beta 2 microglobulin data are available will be conducted as well.

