	• Development of hypercalcemia (corrected serum calcium > 11.5 mg/100 mL) that can be attributed solely to the plasma cell proliferative disorder

Table 7:DEFINITIONS OF RESPONSE AND PROGRESSION CRITERIA
(MODIFIED FROM IMWG)

^a All response categories require 2 consecutive assessments made at any time before the institution of any new therapy; all categories also require no known evidence of progressive or new bone lesions if radiographic studies were performed. Radiographic studies are not required to satisfy these response requirements. Bone marrow assessments need not be confirmed.

^b Note clarification to IMWG criteria for coding CR and VGPR in patients in whom the only measurable disease is by serum FLC levels: CR in such patients is defined as a normal FLC ratio of 0.26-1.65 in addition to CR criteria listed above. VGPR in such patients is defined as a > 90% decrease in the difference between involved and uninvolved FLC levels.

^c Presence or absence of clonal cells is based upon the κ/λ ratio. An abnormal κ/λ ratio by immunohistochemistry and/or immunofluorescence requires a minimum of 100 plasma cells for analysis. An abnormal ratio reflecting presence of an abnormal clone is κ/λ of > 4:1 or < 1:2.

^d For progressive disease, serum M-component increase of ≥ 1 g/dL is sufficient to define progression if starting M-component is ≥ 5 g/dL

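### PFS and OS curves from first dose, split by a response level reached later, build in an advantage for responders, chiefly VGPR or better

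*SAP*

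**What the plan says.** SAP 7.5.1 adds a split of PFS: "PFS is also evaluated based on 3 levels of response (VGPR or better, PR, SD or MR"). SAP 7.5.2 adds the matching split of OS: "OS is also evaluated based on 3 levels of response (VGPR or better, PR, SD or MR"). Both are Kaplan-Meier displays. The PFS analyses are repeated for the primary and secondary PFS definitions, and SAP 7.1 states: "Separate analyses will be conducted for each cohort EPd and EN".

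The clock starts at treatment start for both endpoints. SAP 4.1.3: "Progression Free Survival (PFS) is defined as the time from first dosing date to the date of the first documented progression". SAP 4.3: "Overall Survival (OS) is defined as the time from first dosing date to the date of death from any cause".

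Neither 7.5.1 nor 7.5.2 says how or when a patient is given a response level. The level names match the best overall response categories tabulated in SAP 7.5.3. SAP 4.2 defines that variable: "The best overall response is determined as the best assessment based on all on-study efficacy data for the subject". SAP Appendix 3, footnote a, adds the confirmation rule: "All response categories require 2 consecutive assessments made at any time before the institution of any new therapy". SAP 6.1 sets assessments every 4 weeks. Sections 7.5.1 and 7.5.2 mention no landmark, no time-dependent method and no caution about interpretation.

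**The concern.** If the levels are best overall response, patients are grouped by something that happens after the clock starts. To be counted as PR, and even more as VGPR or better, a patient must remain event-free until the response is reached and confirmed. A patient who would have responded but progresses first is counted as SD/MR, or as PD or unable to determine, which are in none of the three groups. The responder curves therefore begin with a stretch in which no event can occur. This is guarantee-time (immortal-time) bias.

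SD/MR also needs some event-free time, which reduces the bias but does not remove it. What is at stake is interpretation: part of any separation, most clearly for VGPR or better, would be an artefact that a reader could take as evidence that deeper response prolongs PFS or OS.

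**Working it through.** **Inputs from the documents.** SAP 5.1: exponential PFS, median 15 months, N = 60. SAP 5.2: 30% ORR and N = 30 for EN. SAP 6.1: 4-weekly assessment. Appendix 3: confirmation on two consecutive assessments.

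**The plan's own figures.** The display has no stated figure, but the PFS model behind it reproduces. Hazard λ = ln 2/15 = 0.0462 per month. With 24 months' uniform accrual and 24 months' minimum follow-up, expected events = 60 × [1 − (e^(−24λ) − e^(−48λ))/(24λ)] = 60 × [1 − (0.3299 − 0.1088)/1.109] = 48.0, as stated.

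**Assumptions, because the documents give no response timing.** PFS time T is unrelated to response. A fraction p of patients are potential responders. Time to response is uniform from 1 to h months, and confirmation comes 1 month later, at V (uniform from 2 to h + 1). A patient is a responder if potential and T > V, and SD/MR if not a responder and T > 2. Then 1 − 0.5^(2/15) = 8.8% of patients fall in no group.

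**Responders.** An exponential time has no memory, so a responder's T is V plus a fresh time with median 15. The median is close to mean V + 15: 2.5 + 15 = 17.5 (h = 2), 3 + 15 = 18.0 (h = 3), 4.5 + 15 = 19.5 (h = 6).

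**SD/MR, worked for p = 0.6, h = 6.**
- P(T > V) = (e^(−2λ) − e^(−7λ))/(5λ) = (0.9117 − 0.7236)/0.2310 = 0.814.
- Group share = 0.4 × 0.9117 + 0.6 × (0.9117 − 0.8141) = 0.3647 + 0.0586 = 0.4233.
- The median t solves 0.4·e^(−λt) = 0.4233/2, so e^(−λt) = 0.529 and t = 13.8 months.

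**All EPd settings.** Median months, responders vs SD/MR. The rate ratio is the responders' event rate over that of SD/MR with complete follow-up; the true value is 1.

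| Potential responders | Response at 1–2 months | 1–3 months | 1–6 months |
|---|---|---|---|
| 30% | 17.5 vs 16.8 (0.97) | 18.0 vs 16.6 (0.94) | 19.5 vs 16.0 (0.87) |
| 60% | 17.5 vs 16.3 (0.95) | 18.0 vs 15.6 (0.91) | 19.5 vs 13.8 (0.80) |
| 80% | 17.5 vs 15.1 (0.91) | 18.0 vs 13.4 (0.83) | 19.5 vs 9.3 (0.68) |

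In 20,000 simulated 60-patient trials per setting, responders had the longer median in 58%, 66% and 84% (p = 0.6) and in 62%, 73% and 93% (p = 0.8). Without bias this would be 50%.

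**Three levels, as the plan displays them.** Here p = 0.6, and 40–60% of responders deepen to VGPR or better over the following 1–3 or 1–6 months. Simulated medians for the three response timings, in order:
- VGPR or better: 19.5–20.9, 19.9–21.5 and 21.4–22.9 months.
- PR: 13.2–16.3, 13.7–16.7 and 15.1–18.2 months.
- SD/MR: 16.3, 15.6 and 13.8 months.

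VGPR or better is always longest. PR can fall below SD/MR, because the patients who last longer move up a level.

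**A second model** used 4-weekly visits, exponential latent response times and 30–100% able to respond (12 scenarios). The ratio for pooled responders vs SD/MR ran from 0.13 to 0.93, and VGPR or better always had the longest median. The PR median was below SD/MR in 7 of the 12 for PFS. For OS, with an assumed 12-month median survival after progression, one mid-range scenario (60% able to respond) gave 36.6 vs 31.8 months for pooled responders vs SD/MR.

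**EN.** The median of 4 months is assumed, and p is set so that 30% are observed responders. Results: 6.5 vs 5.6 (0.90), 7.0 vs 5.2 (0.81) and 8.3 vs 4.3 (0.62). Crossover is not modelled.

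**Check of the remedy.** With a landmark at 24 weeks (168/30.4375 = 5.52 months), the residual medians are 15.0 vs 15.0 at all three EPd timings. With response as a time-dependent covariate, the rate ratio is 1.00 in the EPd scenarios checked.

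**The case against.** The strongest reply is that little depends on this display. No objective asks whether response predicts PFS or OS, no test between levels is planned, the split is not in the topline list (SAP 9.1), and neither document claims that deeper response prolongs survival. All of that stands and limits the weight of the point. It does not make the curves safe to read, since nothing in 7.5.1 or 7.5.2 warns the reader.

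The best-response reading is also an inference. The sentences say only response, some SAP sections are not in the public copy, and table details are left to a Data Presentation Plan that is not available. This stands too. However, best overall response is the only per-subject on-study response summary visible in the SAP, and no response at a fixed time is defined. If something else was meant, 7.5.1 and 7.5.2 still need to say so.

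The size depends on assumptions and can be small. With 30% potential responders and early response the ratio is 0.97, hardly visible at N = 60. The pooled comparison is not the planned three-curve display, and PR is not consistently favoured. The EN figures rest on an assumed median and ignore crossover, and about 9 responders (30% of 30) split over two levels would say little under any method. These points narrow the claim to VGPR or better and to pooled responders. For those two, the direction was the same in every scenario run.

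**Conclusion.** The concern holds. Read as best overall response, the planned first-dose curves favour VGPR or better, and responders as a whole, even when response has no effect. For EPd the spurious rate ratio for pooled responders vs SD/MR runs from 0.97 to 0.68 over 30–80% potential responders and response within 2 to 6 months; the second model, with wider assumptions, goes lower. For scale, the EPd cohort was sized on a ratio of 0.73. The size rests on response timing and response fraction that the documents do not give; the direction does not. The reach is limited to a descriptive supplementary display, so this is a correction worth making and not a threat to the primary results.

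**What to change.** In SAP 7.5.1 and 7.5.2:

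1. State which response variable defines the three levels and when it is fixed. For EN, say whether responses after crossover to EPd count.
2. Present PFS and OS by response level from a pre-specified landmark, with time measured from it. Include patients in follow-up who are progression-free (PFS) or alive (OS) at that time, classed by confirmed response to date. Set the landmark by cohort, for example 24 weeks for EPd and earlier for EN, where Protocol 3.1 allows crossover after 2 or 5 cycles. Alternatively, fit confirmed response as a time-dependent covariate.
3. Label any first-dose curves that are kept as descriptive and subject to guarantee-time bias.

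The cost is SAP wording and minor programming, with no new data. A landmark at L months drops 1 − 0.5^(L/median) of patients from this display. For EPd at 24 weeks that is 22.5% at a 15-month median and 29.4% at 11 months. About 27% of eventual EPd responders would not yet be confirmed if response comes at 1–6 months, and none if it comes at 1–3 months.

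For EN at an assumed 4-month median, 61.6% drop out at 24 weeks and 38.0% at 12 weeks. At 12 weeks, 22% to 79% of eventual responders are not yet confirmed. The time-dependent model drops nobody, but it gives a hazard ratio instead of simple curves and will be imprecise with about 30 EN patients. If neither suits EN, the definition and the label are the minimum there.
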